#### **7.12.2. EuroQol 5 Dimensions - Youth**

The EQ-5D-Y is a newly developed generic instrument measuring health-related quality of life in children and adolescents 8 years onwards. It was adapted from the EQ-5D original questionnaire (<http://www.euroqol.org/about-eq-5d.html>). It consists of a descriptive system (EQ-5D) of health-related quality of life states, consisting of five dimensions including mobility (walking about), self-care (looking after myself), usual activities (doing usual activities), pain/discomfort (having pain or discomfort), and anxiety/depression (feeling worried, sad or unhappy) each of which can take one of three responses. The responses record three levels of severity (no problems, some problems, or a lot of problems) within a particular ED-5D dimension. Additionally, the EQ-5D consists of a standard vertical 20 cm visual analogue scale (EQ VAS) for recording an individual's rating of their current health-related quality of life state on a scale from 0 to 100 with 0 representing the worst and 100 the best health state he or she can imagine. All items refer to the health state "today." Health state utilities will also be calculated (see [Clinical Outcomes Assessment manual](#)).

## **8. ADVERSE EVENT REPORTING**

### **8.1. Adverse Events**

All observed or volunteered AEs regardless of treatment group or suspected causal relationship to the investigational product(s) will be reported as described in the following sections.

For all AEs, the investigator must pursue and obtain information adequate both to determine the outcome of the AE and to assess whether it meets the criteria for classification as a serious adverse event (SAE) requiring immediate notification to Pfizer or its designated representative. For all AEs, sufficient information should be obtained by the investigator to determine the causality of the AE. The investigator is required to assess causality. Follow-up by the investigator may be required until the event or its sequelae resolve or stabilize at a level acceptable to the investigator, and Pfizer concurs with that assessment.

As part of ongoing safety reviews conducted by the sponsor, any nonserious AE that is determined by the sponsor to be serious will be reported by the sponsor as an SAE. To assist in the determination of case seriousness, further information may be requested from the investigator to provide clarity and understanding of the event in the context of the clinical study.

### **8.2. Reporting Period**

For SAEs, the active reporting period to Pfizer or its designated representative begins from the time that the subject provides informed consent, which is obtained prior to the subject's participation in the study, ie, prior to undergoing any study-related procedure and/or receiving investigational product, through and including 84 calendar days after the last administration of the investigational product. SAEs occurring to a subject after the active reporting period has ended should be reported to the sponsor if the investigator becomes aware of them; at a minimum, all SAEs that the investigator believes have at least a reasonable possibility of being related to investigational product are to be reported to the sponsor.

AEs (serious and non-serious) should be recorded on the case report form (CRF) from the time the subject has taken at least 1 dose of investigational product through the subject's last visit.

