Study Day a	365, 701, 1037	393, 729, 1065	421, 757, 1093	449, 785, 1121	477, 813, 1149	505, 841, 1177	533, 869, 1205	561, 897, 1233	589, 925, 1261	617, 953, 1289	645, 981, 1317	673, 1009, 1345	
Visit Window	± 3 days												
MRI-Liver						X						X	X
DXA-Spine												X	X
DXA-Whole Body												X	X
X-ray (hand and wrist) c												X	X
Functional Assessments													
Ambulatory status m	X	→	→	→	→	→	→	→	→	→	→	X	X
PFTs						X						X	X
4 Stair Climb n					X							X	X
Northstar Ambulatory Assessment n					X							X	X
Range of Motion					X							X	X
Strength Assessment					X							X	X
PUL					X							X	X
6MWT n					X							X	X
Investigational Product Administration													
Investigational Product administration o	X	X	X	X	X	X	X	X	X	X	X		
PK/Immunogenicity													
PK sample p						X						X	X
Immunogenicity					X							X	X
Biobanking Sample (Group 1 and Group 2 Biomarkers)												X	
Infusion Site Reaction monitoring	X	→	→	→	→	→	→	→	→	→	→	→	X
Adverse event monitoring	X	→	→	→	→	→	→	→	→	→	→	→	X
Concomitant medication	X	→	→	→	→	→	→	→	→	→	→	→	X

Abbreviations: → = ongoing/continuous monitoring; 6MWT=Six minute walk test; C-SSRS=Columbia Suicide Severity Rating Scale, DXA=Dual-energy x-ray absorptiometry; ECG = electrocardiogram; EQ-5D-3L=EuroQoL 5 Dimensions 3 Levels; EQ-5D-Y=EuroQoL 5 Dimensions - Youth; FSH= Follicle stimulating hormone; HRU=Healthcare Resource Utilization; LH= Luteinizing hormone; MRI=magnetic resonance image; PD=Pharmacodynamics; PFTs = pulmonary function tests; PK=Pharmacokinetics, PODCI=Pediatric Outcomes Data Collection Instrument; PUL=Performance of Upper Limb, T4 =thyroxine; TIBC=Total

Visit Number a	Year 2,3,4 and Early Withdrawal												
	14 26, 38	15, 27, 39	16 28, 40	17, 29, 41	18, 30, 42	19, 31, 43	20, 32, 44	21, 33, 45	22, 34, 46	23, 35, 47	24, 36, 48	25, 37, 49	Early Withdrawal
Study Week a	53, 101, 149	57, 105, 153	61, 109, 157	65, 113, 161	69 117, 165	73, 121, 169	77, 125, 173	81, 129, 177	85, 133, 181	89, 137, 185	93, 141, 189	97, 145, 193	
Study Day a	365, 701, 1037	393, 729, 1065	421, 757, 1093	449, 785, 1121	477, 813, 1149	505, 841, 1177	533, 869, 1205	561, 897, 1233	589, 925, 1261	617, 953, 1289	645, 981, 1317	673, 1009, 1345	
Visit Window	± 3 days												

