Visit Number a	Year 2,3,4 and Early Withdrawal												Early Withdrawal
	14 26, 38	15, 27, 39	16, 28, 40	17, 29, 41	18, 30, 42	19, 31, 43	20, 32, 44	21, 33, 45	22, 34, 46	23, 35, 47	24, 36, 48	25, 37, 49	
Study Week a	53, 101, 149	57, 105, 153	61, 109, 157	65, 113, 161	69 117, 165	73, 121, 169	77, 125, 173	81, 129, 177	85, 133, 181	89, 137, 185	93, 141, 189	97, 145, 193	
Study Day a	365, 701, 1037	393, 729, 1065	421, 757, 1093	449, 785, 1121	477, 813, 1149	505, 841, 1177	533, 869, 1205	561, 897, 1233	589, 925, 1261	617, 953, 1289	645, 981, 1317	673, 1009, 1345	
Visit Window	± 3 days												

reported data they can still participate in the study.

- m. Ambulatory status should be reviewed at each visit. Ambulation is defined as the ability to walk unassisted and without braces for at least 10 m. If a subject becomes non-ambulatory this should be recorded in the CRF.
- n. If a loss of ambulation has occurred 4 Stair Climb, Northstar Ambulatory Assessment and 6MWT do not need to be completed. Please record date that ambulation was lost.
- o. Investigational product should be delivered in a 2 hour window ±15 minutes including the flush time. If a dosing visit cannot be conducted within the visit window, attempts should be made to bring the subject back for dosing as soon as possible; however the dosing **must not occur** within 2 weeks prior to the next scheduled dose. If the subject cannot return in this timeframe, the dose should be missed and the next visit should be conducted per the [Schedule of Activities](#).
- p. PK samples to be taken prior to dosing.

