## **2.2. Endpoints**

### **2.2.1. Primary endpoints**

#### **2.2.1.1. Safety**

- Incidence and/or rate of intolerance or dose limiting treatment related AEs following up to 4 years of treatment.
- Incidence and/or rate, severity and causal relationship of TEAEs and withdrawals due to TEAEs following up to 4 years of treatment.
- Incidence and magnitude of abnormal laboratory findings (clinical laboratory tests: hematology, chemistry, GGT, GLDH, PT, aPTT, creatine kinase, amylase, serum ferritin, serum iron, total iron binding capacity (TIBC), % transferrin saturation. Hormones: luteinizing hormone [LH], follicle stimulating hormone [FSH], thyroxine [T4], thyroid stimulating hormone [TSH]. Fecal occult blood, cardiac Troponin I and urinalysis) following up to 4 years of treatment.
- Abnormal and clinically relevant changes in liver MRI and physical examinations (including nose and throat mucosal exam and Tanner stage and Testicular Volume), weight, vitals, electrocardiogram (ECG), LVEF measured by cardiac MRI (or echocardiogram), bone mineral density by DXA, x-ray (hand and wrist for bone age evaluation) and C-SSRS.

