- d. Determination of “yes” on the question of Actual Attempt, Interrupted Attempt, Aborted Attempt, or Preparatory Acts or Behavior for Suicidal Behavior section of C-SSRS.
- e. Acute suicidality to such a degree that precaution against suicide must be exercised.

At the time of withdrawal, procedures outlined in the early withdrawal visit should be performed as detailed in the [Schedule of Activities](#) and [Assessments](#).

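### Section 8.2 ends CRF recording of all AEs, serious ones included, at the last visit, while SAE reporting runs to 84 days after the last dose; the two windows are not reconciled.

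*Protocol*

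**What the plan says.** Section 8.2 of the Protocol (Reporting Period) defines two windows in consecutive paragraphs.

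- **SAE reporting to the sponsor** "begins from the time that the subject provides informed consent" and runs "through and including 84 calendar days after the last administration of the investigational product". SAEs that the investigator learns of later are also to be reported, at a minimum those thought possibly related.
- **CRF recording of AEs**, stated to cover both serious and non-serious events, runs "from the time the subject has taken at least 1 dose of investigational product through the subject's last visit".

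Four other places bear on this.

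- Section 2.2.1.1 makes the incidence, severity and "causal relationship of TEAEs and withdrawals due to TEAEs following up to 4 years of treatment" a primary endpoint.
- Section 8.14.2 sends every AE to the AE pages of the CRF. It notes that the SAE form is a separate form and requires the two to agree where they hold the same data.
- Section 8.6.1 lists events expected in DMD, among them fracture, loss of ambulation and respiratory muscle weakness or hypoxia. Investigators are not to report these as SAEs unless they believe the drug caused them. The CRF is named as the place where they are still captured.
- The flowchart for Years 2 to 4 marks the last infusion in the Week 189 column. Week 193 is the last visit, and no safety follow-up visit comes after it.

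**The concern.** Safety is the primary objective, and the sponsor chose 84 days after the last dose, three 4-week dosing intervals, as the period in which serious events matter enough to be actively reported. The CRF closes earlier without explanation. Because the CRF sentence names serious events, the difference cannot be read as applying to non-serious AEs alone.

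Two groups of events are affected. SAEs after the last visit arrive on the SAE form with no matching CRF record. New Section 8.6.1 events after the last visit, if not believed drug-related, belong on neither form. Section 8.6.1 depends on aggregate analysis to show whether such events occur more often than expected, and Sections 1.6.4 and 7.9 single out bone for monitoring. An unrelated-judged fracture 40 days after the last dose would not be available to that analysis.

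**Working it through.** The Protocol gives no figure for the uncovered period, so there is none to reproduce. The check is calendar arithmetic.

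**Inputs**

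- SAE reporting ends 84 days after the last dose (Section 8.2).
- The last marked infusion is Visit 48, Week 189, Day 1317, and the last visit is Visit 49, Week 193, Day 1345 (flowchart, Years 2 to 4).
- The visit window is ±3 days (same flowchart).
- The previous infusion is Week 185, Day 1289 (same flowchart).
- Missed doses are allowed: "If the subject cannot return in this timeframe, the dose should be missed and the next visit should be conducted per the" schedule (flowchart footnote on dosing).
- Early withdrawal: "At the time of withdrawal, procedures outlined in the early withdrawal visit should be performed" (Section 6.3), with no interval from the last dose specified.

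**Check of the calendar.** Study day = (week − 1) × 7 + 1. Week 189: 188 × 7 + 1 = 1317. Week 193: 192 × 7 + 1 = 1345. Both match the flowchart.

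**Formula.** Days after CRF closure but inside SAE reporting = 84 − (day of last visit − day of last dose).

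| Situation | Last dose | Last visit | Gap | Days outside CRF | Share of 84 |
|---|---|---|---|---|---|
| On schedule | 1317 | 1345 | 28 | 56 | 66.7% |
| Dose 3 days early, visit 3 days late | 1314 | 1348 | 34 | 50 | 59.5% |
| Dose 3 days late, visit 3 days early | 1320 | 1342 | 22 | 62 | 73.8% |
| Week 189 dose missed | 1289 | 1345 | 56 | 28 | 33.3% |
| Week 189 dose given 14 days late | 1331 | 1345 | 14 | 70 | 83.3% |
| Early withdrawal | not fixed | not fixed | – | not fixed | – |

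The 14-day-late row assumes that the two-week limit before the next scheduled dose is counted from the Week 193 slot.

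**Scale against the whole study.** From first dose to the end of SAE reporting is 1317 + 84 = 1401 days for an on-schedule completer. The uncovered part is 56 / 1401 = 4.0%, all of it after treatment has stopped. The share is larger for boys who leave early with the same gap.

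**What happens to each type of event after the last visit**

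| Event | SAE form | CRF |
|---|---|---|
| SAE not on the 8.6.1 list | yes, to day 84 | no (8.2), though 8.14.2 requires it |
| 8.6.1 event believed drug-related and serious | yes, to day 84 | no (8.2) |
| 8.6.1 event not believed drug-related | no (8.6.1) | no (8.2), though 8.6.1 requires it |
| New non-serious AE | not applicable | no (8.2) |

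**Start points.** These differ too. SAE reporting starts at consent, which Section 6.1 places before the parent study's Week 97 assessments; CRF recording starts at first dose. An SAE during screening (window up to 42 days) has no CRF entry either.

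**The case against.** The strongest reply is that little is lost. Serious events are actively reported to day 84, and related ones after that. AEs already open are followed after withdrawal (Section 6.3) and, where required, until resolved or stable (Section 8.1). A shorter window for non-serious AEs than for SAEs is a legitimate design choice. The uncovered days are off drug and about 4% of the period for a completer. The definition of TEAE and the data source for the tables commonly belong in the SAP. All of this stands, and it limits the point. It does not answer the conflict of Section 8.2 with Sections 8.14.2 and 8.6.1, and follow-up of open AEs does not capture new ones.

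A reader might infer more than the Protocol supports:

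- **That at least 56 days are always lost.** This is not a lower bound. The visit windows allow 50, a missed Week 189 dose gives 28, and early withdrawal has no fixed interval. An unplanned visit could also move the last visit later.
- **That all 84 days are lost because the last dose falls on the last visit.** The dosing row is blank at Week 193 and at Early Withdrawal. If Week 193 were in fact dosed, the figure would be 84, but the table as it reads does not show that.
- **That the primary TEAE results omit late SAEs and are understated.** Section 9.2 names neither a data source nor a TEAE window, and the SAP may bring in SAEs from the safety database.

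**Conclusion.** The point holds as a correctable inconsistency in how primary-endpoint data are captured. For a boy on schedule, nominally 56 of the 84 days of active SAE reporting (50 to 62 within the visit windows) come after CRF recording has closed. In that time SAEs have no CRF entry, and Section 8.6.1 events not believed drug-related have no recording route. The second loss is the firmer one, because no later analysis plan can recover events that were never recorded. Sponsor withdrawal of subjects, which Section 3.2 allows, could expose many boys to it at once, over an interval that the Protocol does not fix.

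The day counts assume that the flowchart's blank dosing cell at Week 193 is correct and that the last visit is the scheduled one. Any effect on the reported TEAE incidence is unknown: the Protocol does not say whether late SAEs are added to the tables.

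**What to change.** In Section 8.2, extend CRF recording of SAEs and of Section 8.6.1 events to 84 days after the last dose, matching the SAE reporting period. State that these events are included in the safety summaries, shown separately as post-treatment follow-up if preferred. In the same revision, reconcile the start points (consent for SAEs, first dose for the CRF), and make Sections 8.6.1 and 8.14.2 refer to the agreed window.

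The cost is Protocol and CRF wording, some extra data entry (the SAEs already reach the sponsor), and a slightly later database lock. A telephone contact at day 84 to collect non-serious AEs would be a further option, but it adds a contact and is not part of the change needed.

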### **8.3. Definition of an Adverse Event**

An AE is any untoward medical occurrence in a clinical investigation subject administered a product or medical device; the event need not necessarily have a causal relationship with the treatment or usage. Examples of AEs include but are not limited to:

- Abnormal test findings.
- Clinically significant symptoms and signs.

- Changes in physical examination findings.
- Hypersensitivity.
- Progression/worsening of underlying disease.
- Drug abuse.
- Drug dependency.

Additionally, they may include the signs or symptoms resulting from:

- Drug overdose.
- Drug withdrawal.
- Drug misuse.
- Drug interactions.
- Extravasation.
- Exposure during pregnancy (EDP).
- Medication error.
- Occupational exposure.

#### **8.4. Medication Errors**

Medication errors may result, in this study, from the administration or consumption of the wrong product, by the wrong subject, at the wrong time, or at the wrong dosage strength. Such medication errors occurring to a study participant are to be captured on the medication error CRF, which is a specific version of the AE page, and on the SAE form when appropriate. In the event of medication dosing error, the sponsor should be notified immediately.

Medication errors are reportable irrespective of the presence of an associated AE/SAE, including:

- Medication errors involving subject exposure to the investigational product.
- Potential medication errors or uses outside of what is foreseen in the protocol that do or do not involve the participating subject.

Whether or not the medication error is accompanied by an AE, as determined by the investigator, the medication error is captured on the medication error version of the AE page and, if applicable, any associated AE(s) are captured on an AE CRF page.

### **8.5. Abnormal Test Findings**

The criteria for determining whether an abnormal objective test finding should be reported as an AE are as follows:

- Test result is associated with accompanying symptoms; and/or
- Test result requires additional diagnostic testing or medical/surgical intervention; and/or
- Test result leads to a change in study dosing (outside of protocol-stipulated dose adjustments) or discontinuation from the study, significant additional concomitant drug treatment, or other therapy; and/or
- Test result is considered to be an AE by the investigator or sponsor.

Merely repeating an abnormal test, in the absence of any of the above conditions, does not constitute an AE. Any abnormal test result that is determined to be an error does not require reporting as an AE.

### **8.6. Serious Adverse Events**

A serious adverse event is any untoward medical occurrence at any dose that:

- Results in death.
- Is life-threatening (immediate risk of death).
- Requires inpatient hospitalization or prolongation of existing hospitalization.
- Results in persistent or significant disability/incapacity (substantial disruption of the ability to conduct normal life functions).
- Results in congenital anomaly/birth defect.

Medical and scientific judgment is exercised in determining whether an event is an important medical event. An important medical event may not be immediately life-threatening and/or result in death or hospitalization. However, if it is determined that the event may jeopardize the subject or may require intervention to prevent one of the other AE outcomes, the important medical event should be reported as serious.

Examples of such events are intensive treatment in an emergency room or at home for allergic bronchospasm; blood dyscrasias or convulsions that do not result in hospitalization; or development of drug dependency or drug abuse.

### **8.6.1. Protocol-Specified Serious Adverse Events**

Unless the investigator believes that there is a causal relationship between the investigational product and an event specified below, these events should not be reported by the investigator as SAEs as described in the [Serious Adverse Event Reporting Requirements](#) section of this protocol. These events are anticipated to occur commonly in a population with DMD. However, these events should still be captured as AEs in the CRF.

Protocol-specified events that will not normally be reported in an expedited manner:

- a. Loss of mobility or ambulation.
- b. Muscle weakness.
- c. Symptoms related to spinal deformity.
- d. Respiratory muscle weakness/Hypoxia.
- e. Fracture.
- f. Steroid related metabolic changes (Hypertension, diabetes).

Should an aggregate analysis indicate that these pre-specified events occur more frequently than expected based on the expectation of frequency of the event(s) in question in the population for comparison, eg, based on epidemiological data, literature, or other data, then this will be submitted and reported in accordance with Pfizer's safety reporting requirements. Aggregate analysis of safety data will be performed on a regular basis per internal standard operating procedures and on a quarterly basis by the E-DMC.

### **8.6.2. Potential Cases of Drug-Induced Liver Injury**

Abnormal values in aspartate aminotransferase (AST) and/or alanine aminotransferase (ALT) levels concurrent with abnormal elevations in total bilirubin level that meet the criteria outlined below in the absence of other causes of liver injury are considered potential cases of drug-induced liver injury (potential Hy's law cases) and should always be considered important medical events.

The threshold of laboratory abnormalities for a potential case of drug-induced liver injury depends on the subject's individual baseline values and underlying conditions. Subjects who present with the following laboratory abnormalities should be evaluated further to definitively determine the etiology of the abnormal laboratory values:

- Subjects with AST or ALT and total bilirubin baseline values within the normal range who subsequently present with AST or ALT values  $\geq 3$  times the upper limit of normal ( $\times$  ULN) concurrent with a total bilirubin value  $\geq 2 \times$  ULN with no evidence of hemolysis and an alkaline phosphatase value  $\leq 2 \times$  ULN or not available.

- For subjects with preexisting ALT **OR** AST **OR** total bilirubin values above the ULN, the following threshold values should be used in the definition mentioned above:
  - For subjects with preexisting AST or ALT baseline values above the normal range: AST or ALT values  $\geq 2$  times the baseline values and  $\geq 3 \times$  ULN, or  $\geq 8 \times$  ULN (whichever is smaller).

Concurrent with:

- For subjects with preexisting values of total bilirubin above the normal range: Total bilirubin level increased from baseline by an amount of at least  $1 \times$  ULN or if the value reaches  $\geq 3 \times$  ULN (whichever is smaller).

The subject should return to the investigational site and be evaluated as soon as possible, preferably within 48 hours from awareness of the abnormal results. This evaluation should include laboratory tests, detailed history, and physical assessment.

In addition to repeating measurements of AST and ALT, laboratory tests should include albumin, creatine kinase, total bilirubin, direct and indirect bilirubin, GGT, GLDH, PT/INR, and alkaline phosphatase. A detailed history, including relevant information, such as review of ethanol, acetaminophen, recreational drug and supplement consumption, family history, occupational exposure, sexual history, travel history, history of contact with a jaundiced person, surgery, blood transfusion, history of liver or allergic disease, and work exposure, should be collected. Further testing for acute hepatitis A, B, or C infection and liver imaging (eg, biliary tract) may be warranted. All cases confirmed on repeat testing as meeting the laboratory criteria defined above, with no other cause for liver function test (LFT) abnormalities identified at the time, should be considered potential Hy's law cases irrespective of availability of all the results of the investigations performed to determine etiology of the abnormal LFTs. Such potential Hy's law cases should be reported as SAEs.

